5.1 Definitions

An AE is defined as any untoward medical occurrence in a patient or clinical trial subject administered a medicinal product and which does not necessarily have a causal relationship with this treatment. AEs would not include information recorded as medical history at screening for pre planned procedures for which the underlying condition was known and no worsening occurred. An adverse reaction is any untoward and unintended response to an IMP related to any dose administered.

A suspected adverse reaction is any AE for which there is a reasonable possibility that the IMP caused the AE.

An SAE includes any event that results in any of the following outcomes:

- Death
- Life-threatening; ie, the subject was, in the opinion of the investigator or subinvestigator, at immediate risk of death from the event as it occurred. It does not include an event that, had it occurred in a more severe form, might have caused death.
- Persistent or significant incapacity/disability or substantial disruption of the ability to conduct normal life functions.
- Requires in-patient hospitalization or prolongs hospitalization.
 - Hospitalization itself should not be reported as an SAE; whenever possible the reason for the hospitalization should be reported.

- Hospitalizations or prolonged hospitalizations for social admissions (ie, those required for reasons of convenience or other non-medical need) are not considered SAEs.
- Congenital anomaly/birth defect.
- Other medically significant events that, based upon appropriate medical judgment, may jeopardize the subject and may require medical or surgical intervention to prevent one of the outcomes listed above; eg, allergic bronchospasm requiring intensive treatment in an emergency room or home, blood dyscrasias or convulsions that do not result in hospitalization, or the development of drug dependency or drug abuse.

Nonserious adverse events are all AEs that do not meet the criteria for a "serious" AE. Immediately Reportable Event (IRE):

- Any SAE.
- Any AE related to occupational exposure.
- Potential Drug Induced Liver Injury (DILI) case (see Section 5.4).
- Pregnancies are also defined as IREs. Although normal pregnancy is not an AE, it will mandate IMP discontinuation and must be reported on an IRE form to the sponsor. Pregnancy will only be documented on the AE CRF if there is an abnormality or complication.

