3.4 Handling of Time Points

CRF Visit values at each time point (run-in period, treatment period, and follow-up) will be used in summaries (but values at the time of discontinuation will not be used in summaries). Unscheduled Visit values will not be used.

Baseline and final administration time point for each variable are defined as follows.

Variable	Baseline ^a	Final Administration Time Point
Body weight	Before IMP administration on Day 1	Day after final IMP administration
Congestive symptoms	Run-in period (final measurement)	Day after final IMP administration
Pulmonary congestion, cardiothoracic ratio	Run-in period	Day after final IMP administration
NYHA classification	Run-in period	Day after final IMP administration
Clinical laboratory value	Before IMP administration on Day 1	Day after final IMP administration
Vital signs	Before IMP administration on Day 1	Day after final IMP administration
12-lead ECG	Run-in period	Day after final IMP administration
Serum sodium concentration, serum potassium concentration, serum osmolality, biomarker	Before IMP administration on Day 1	-
Daily urinary output, daily fluid intake, daily water balance, daily sodium urinary excretion, daily potassium urinary excretion, urinary osmolality	During 24 hours before start of IMP administration on Day 1	-

^aWhen multiple data are collected during the run-in period, the data closest to Day 1 will be used as baseline.

4 Sample Size

The primary objective of this clinical trial is to compare tolvaptan exposure in order to investigate the dose of OPC-61815 injection required to achieve exposure equivalent to tolvaptan 15-mg tablet for use in conducting phase 3 confirmatory clinical trials of OPC-61815. The number of subjects required for this purpose was determined to be at least 10 subjects per group (50 subjects in total) who complete blood sampling for measurement of plasma drug concentrations up until 24 hours postdose on Day 1. In consideration of the possibility of some subjects withdrawing from the trial prior to 24 hours postdose on Day 1, the approximate target number of subjects for the start of IMP administration is set at 11 subjects per group (55 subjects in total).

5 Statistical Analysis Sets

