9.3 Clinical Laboratory Data

For hematology, serum chemistry (excluding PAP and TRACP-5b), and urinalysis in the protocol “Table 3.7.4.2-1 Clinical Laboratory Assessments” (at the central laboratory), the following will be summarized.

Descriptive statistics of clinical laboratory values (excluding qualitative urinalysis other than pH) as well as of the changes from baseline in values at each time point and after final administration will be calculated. The results of qualitative urinalysis at each postdose time point and after final administration compared with baseline results will be summarized in a shift table. Each clinical laboratory value excluding qualitative urinalysis will be categorized into “within reference range,” “below the lower limit of reference range,” or “above the upper limit of reference range” using the institutional standard values to generate a shift table summarizing laboratory data at each postdose time point and after final administration compared with baseline.

For parameters excluding qualitative urinalysis, a scatter diagram of values after the final administration with comparison to baseline will be created in each group.

For presence or absence of an elevation in AST or ALT that is ≥ 3 times the upper limit of normal of the institutional standard values as well as an elevation in total bilirubin ≥ 2 times the upper limit of normal of the institutional standard values at any point after IMP administration, the number and percentage of subjects will be calculated.

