- CT-9.4 Incidences of Potentially Drug-related Serious Treatment-emergent Adverse Events by MedDRA System Organ Class and Preferred Term (Safety Analysis Set)
- CT-9.5 Incidences of Treatment-emergent Adverse Events Leading to Discontinuation of Investigational Medicinal Product Administration by MedDRA System Organ Class and Preferred Term (Safety Analysis Set)

CT-9.6 Incidences of Potentially Drug-related Treatment-emergent Adverse Events Leading to Discontinuation of Investigational Medicinal Product Administration by MedDRA System Organ Class and Preferred Term (Safety Analysis Set)

CT-9.7 Listing of Deaths (Safety Analysis Set)

CT-9.8 Listing of Subject With Serious Adverse Events Other Than Death (Safety Analysis Set)

CT-9.9 Listing of Subject With Adverse Events Leading to Discontinuation of Investigational Medicinal Product Administration (Safety Analysis Set)

CT-10.1.1 Mean Change from Baseline in Clinical Laboratory Test Results (Serum Chemistry) (Safety Analysis Set)

CT-10.1.2 Mean Change from Baseline in Clinical Laboratory Test Results (Hematology) (Safety Analysis Set)

CT-10.1.3 Mean Change from Baseline in Clinical Laboratory Test Results (Urinalysis) (Safety Analysis Set)

CT-10.2 Shift Tables of Clinical Laboratory Test Results (Qualitative Urinalysis) (Safety Analysis Set)

CT-10.3.1 Shift Tables of Clinical Laboratory Test Results (Serum Chemistry) (Safety Analysis Set)

CT-10.3.2 Shift Tables of Clinical Laboratory Test Results (NA, K) (Safety Analysis Set)

CT-10.3.3 Shift Tables of Clinical Laboratory Test Results (Hematology) (Safety Analysis Set)

CT-10.3.4 Shift Tables of Clinical Laboratory Test Results (Urinalysis) (Safety Analysis Set)

CT-10.4.1 Listing of Abnormal Laboratory Findings (Safety Analysis Set)

CT-10.4.2 Listing of Abnormal Laboratory Findings Potential Drug-Induced Liver Injury (Randomized Subjects)

CT-10.5 Incidence of Potential Drug-Induced Liver Injury (Safety Analysis Set)

CT-11 Mean Change from Baseline in Vital Signs (Safety Analysis Set)

CT-12.1 Mean Change from Baseline in Electrocardiogram Results (Safety Analysis Set)

CT-12.2 Shift Table of 12-Lead ECG Findings (Normal/Abnormal Assessments) (Safety Analysis Set)

CT-12.3.1 Incidence of Categorical Changes in Electrocardiogram Results in All Visits (Safety Analysis Set)

CT-12.3.2 Incidence of Categorical Changes in Electrocardiogram Results at Baseline (Run-in Period) (Safety Analysis Set)

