Appendix 2 List of Subject Data

AE-1	Adverse Events (Randomized Subjects)
AE-2	Adverse Events Observed Before Start of Investigational Medicinal Product Administration (Randomized Subjects)
DEMOG-1	Demographic and Baseline Characteristics (Randomized Subjects)
DREAS-1	Discontinued Subjects and Reason for Discontinuation (Randomized Subjects)
LAB-1.1	Laboratory Test Results - Serum Chemistry (Randomized Subjects)
LAB-1.2	Laboratory Test Results - Serum Chemistry (from ADaM) (Randomized Subjects)
LAB-2.1	Laboratory Test Results - Hematology (Randomized Subjects)
LAB-2.2	Laboratory Test Results - Hematology (from ADaM) (Randomized Subjects)
LAB-3.1	Laboratory Test Results - Urinalysis (Randomized Subjects)
LAB-3.2	Laboratory Test Results - Urinalysis (from ADaM) (Randomized Subjects)
LAB-4	Laboratory Test Results - Serum Sodium Trial Site (Randomized Subjects)
PDEV-1	Protocol Deviations (Randomized Subjects)
SMED-1	Investigational Medicinal Product Compliance Injection (Randomized Subjects)
SMED-2	Investigational Medicinal Product Compliance Injection (Full Administration / Interruption) (Randomized Subjects)
SMED-3	Investigational Medicinal Product Compliance Tablet (Randomized Subjects)
SUBEX-1	Subjects Excluded From Analysis Set (Randomized Subjects)
PDATA-1	Study Completion Status and Reason for Discontinuation (Randomized Subjects)
PDATA-2	Inclusion Criteria and Exclusion Criteria Not Met (Randomized Subjects)

- PDATA-3.1 Medical History and Complications (Randomized Subjects)
- PDATA-3.2 History of Congestive Heart Failure (Randomized Subjects)
- PDATA-4.1 Concomitant Medications (Randomized Subjects)
- PDATA-4.2 Concomitant Therapy Other Than Medication (Randomized Subjects)
- PDATA-5.1.1 Vital Signs (Randomized Subjects)
- PDATA-5.1.2 Vital Signs (from ADaM) (Randomized Subjects)
- PDATA-5.2 Body Weight and Height (Randomized Subjects)
- PDATA-6.1.1 Electrocardiogram Results Central ECG Analysis Laboratory (Randomized Subjects)
- PDATA-6.1.2 Electrocardiogram Results Central ECG Analysis Laboratory (from ADaM) (Randomized Subjects)
- PDATA-6.2.1 Electrocardiogram Results Trial Site (Randomized Subjects)
- PDATA-6.2.2 Electrocardiogram Results Trial Site (from ADaM) (Randomized Subjects)
- PDATA-7 Pharmacokinetic Blood Draw Time (Randomized Subjects)
- PDATA-8 Screen Failures
- PDATA-9 Physical Examination (Randomized Subjects)
- PDATA-10 Serum Sodium Concentration, Serum Potassium Concentration (Randomized Subjects)

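### The SAP does not say whether its exclusion of discontinuation and unscheduled values applies to the liver-elevation count or to the final-administration value, and its carry-forward rule lets a pre-dose baseline stand as the final value

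*SAP*

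**What the plan says.** **Time points.** SAP 3.4 takes CRF visit values from run-in, treatment and follow-up into the summaries, and then states: "but values at the time of discontinuation will not be used in summaries). Unscheduled Visit values will not be used". The table beneath sets the final administration time point as the day after the last dose for body weight, congestive symptoms, chest X-ray measures, NYHA class, laboratory values, vital signs and ECG.

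**Liver count.** For descriptive statistics on central-laboratory data, SAP 9.3 says "the changes from baseline in values at each time point and after final administration will be calculated". For AST/ALT ≥3×ULN and total bilirubin ≥2×ULN it uses different words: "at any point after IMP administration, the number and percentage of subjects will be calculated". The planned output is table CT-10.5, "Incidence of Potential Drug-Induced Liver Injury (Safety Analysis Set".

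**Discontinuation examination.** Protocol 3.7.1.8 asks a subject who stops early to have the end-of-trial tests on the day after the last dose, if possible. Table 3.7-1 puts the two examinations in one column.

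**Missing data.** Under SAP 5.5 and Protocol 7.3, if the measurement on the day after the last dose is missing, the last earlier observation is carried forward. Neither requires that observation to be post-dose.

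**The concern.** Three things are left open or go wrong.

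1. SAP 3.4 and SAP 9.3 give different answers on which laboratory values enter the liver count, and neither refers to the other. Two programmers could produce different versions of CT-10.5 from the same data.
2. For an early withdrawal, the discontinuation examination falls on the day that SAP 3.4 defines as final. The sentence above that table, read literally, removes the value.
3. Where the examination is not done, carry-forward can reach back to the baseline itself.

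At stake is a planned safety summary in the first heart failure patients to receive the drug (Protocol 1.3), together with the final-value summaries of some secondary measures.

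**Working it through.** The plan gives no figure to reproduce, so the check is mainly a trace of the schedule.

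**Step 1. Where can a post-dose AST, ALT or bilirubin value come from?** (Protocol 3.7.1.4 to 3.7.1.9 and 5.1)

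| Source | Full chemistry | Under SAP 3.4 read literally |
|---|---|---|
| Day 1 after dosing | No (sodium and potassium only) | – |
| Days 2–5 | No (sodium and potassium only) | – |
| Repeat or additional test (Protocol 5.1) | If taken | Not used |
| Discontinuation examination | Yes, if possible | Not used |
| Day 6 examination in a completer | Yes | Used |
| Follow-up, 7–10 days after last dose | Yes | Used |

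Each subject has 2 scheduled post-dose panels. A completer keeps 2 of 2. For an early withdrawal, the literal reading keeps 1 of 2, the follow-up panel. Before a completed Day 6 visit, every possible post-dose AST/ALT value comes from a source that SAP 3.4 bars. AST or ALT ≥3×ULN is itself a listed reason for stopping treatment (Protocol 3.8.3.1), so the count and the barred sources concern the same subjects.

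**Step 2. Size per omitted subject.** Inputs: 11 subjects per arm starting treatment (SAP 4); a pooled OPC-61815 column (SAP 9) of 4 × 11 = 44.

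- One arm: 1/11 = 9.1 percentage points.
- Pooled: 1/44 = 2.3 percentage points.

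The subject is omitted only if the value is no longer raised at follow-up.

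**Step 3. Final value.** The SAP 3.4 table and Protocol 3.7.1.8 name the same day. The table therefore takes the value in, while the literal sentence takes it out. The output list has separate ECG tables for Day 6 (CT-12.3.5) and Last Visit (CT-12.3.6), which suggests that discontinuation values stay out of the nominal-day table but feed the last-visit one. It is not conclusive, because carry-forward alone would also make the two tables differ.

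**Step 4. Carry-forward when the examination was not done.** The last earlier scheduled observation is:

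- chemistry and haematology other than sodium and potassium: Day 1 pre-dose, which is the baseline;
- cardiothoracic ratio, pulmonary congestion and NYHA class: run-in, which is the baseline;
- ECG: normally Day 1 or Day 3 post-dose, so largely unaffected;
- body weight and vital signs: measured daily, so largely unaffected.

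In the first two groups, change = baseline − baseline = 0. With one such subject among 11 and mean change *m* in the other ten, the descriptive mean change of a laboratory value after final administration is (10*m* + 0)/11 = 0.91*m*. This factor does not carry over to the analysis of covariance for cardiothoracic ratio. In the NYHA and pulmonary congestion shift tables, the subject is one unchanged entry.

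**The case against.** **The specific wording governs.** SAP 9.3 uses by-visit language for its descriptive statistics and the broader phrase only for the liver count. A reader could fairly take the latter as an intended exception. This is the likelier reading, and a reader who infers that the SAP *will* drop liver cases goes further than the text allows. What stands is that the SAP does not say so and SAP 3.4 contains no exception.

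**The cases are recorded elsewhere.** A laboratory value that leads to discontinuation is an adverse event (Protocol 5.1). The same section lists as immediately reportable "Potential Drug Induced Liver Injury (DILI) case (see Section 5.4". Protocol 5.4 requires bilirubin to be checked when AST/ALT is ≥3×ULN and, if it is ≥2×ULN, a report listing all values plus an adverse event entry. Listings CT-10.4.2 and LAB-1.1 show findings by subject, and the first part of the SAP 3.4 exclusion speaks of summaries, not listings. This limits the harm substantially. The exposed case is an isolated AST/ALT rise first seen at the discontinuation examination of someone who stopped for another reason. It becomes an adverse event only if judged medically relevant or serious.

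**An excluded value is not a missing one.** A reader might infer that SAP 3.4 turns every early withdrawal's final value into a carried-forward baseline. The documents do not support that. SAP 5.5 applies when the measurement is missing, and nothing says that a collected but excluded value counts as missing. The carry-forward point therefore rests only on examinations that were not done.

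**Locally tested samples.** One might add that elevations known only from a site test would escape a central-laboratory count. Protocol 3.7.4.2 sends laboratory samples for central testing and specifies only serum sodium at the site, so no such liver data are planned.

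**Silence in SAP 14.** The protocol has no rule on these values, so SAP 3.4 fills a gap and does not reverse anything. Its absence from SAP 14 is at most a missing clarification.

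**Conclusion.** The point holds as an unresolved ambiguity in two places and a rule with a poor consequence in a third.

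- **Liver count:** SAP 9.3 probably prevails. A literal application of SAP 3.4 would leave out of CT-10.5 a subject whose elevation was seen only on an unscheduled sample or at the discontinuation examination. The effect is 9.1 percentage points per subject in an arm of 11 and 2.3 in the pooled 44.
- **Final value:** the two passages conflict only on a literal reading. The output list favours using the discontinuation examination, but the text does not settle it.
- **Carry-forward:** when the examination is not done, no change follows by construction for the measures in Step 4. This needs no assumption about how SAP 3.4 is read.

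The sizes assume one affected subject and the planned group sizes. The documents give no withdrawal or event rate, so the overall effect cannot be estimated. The primary endpoint (Day 1 Cmax and AUC24h) is unaffected, and SAP 8 declares the efficacy analyses exploratory. The SAP should be corrected, but the dose-finding conclusion is not at risk.

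**What to change.** (a) **SAP 3.4:** limit the exclusion of discontinuation and unscheduled values to nominal-day summaries. State that a discontinuation examination done the day after the last dose supplies the final-administration value.

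(b) **SAP 9.3 and 9.5:** state that the liver threshold counts use all post-dose central-laboratory values, including unscheduled and discontinuation ones. Apply the same rule to the QTc count of subjects exceeding a threshold at one or more post-dose time points.

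(c) **SAP 5.5:** carry forward post-dose observations only, and otherwise leave the final value missing. Record this departure from Protocol 7.3 in SAP 14.

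The cost is a few sentences, one SAP 14 entry and a flag in the analysis dataset. No new data are needed, since central results already reach the sponsor electronically. The downside of (c) is slightly fewer subjects with a final value.

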5.1 Pharmacokinetic Analysis Set

The pharmacokinetic analysis set will include all subjects treated with the IMP at least once and have at least one evaluable plasma drug concentration measurement (other than

Not Analyzed [NA] and Not Determined [ND]) after IMP administration. Subjects who withdrew from the trial or had missing data will also be included. Subjects whose entire data were rejected in Section 102a) will not be included.

5.2 Efficacy Analysis Set

The efficacy analysis set will include all subjects treated with the IMP at least once and have body weight data after IMP administration.

5.3 Safety Analysis Set

The safety analysis set will include all subjects treated with the IMP at least once.

5.4 Pharmacodynamic Analysis Set

The pharmacodynamic analysis set will include all subjects treated with the IMP at least once and have pharmacodynamic data after IMP administration.

5.5 Handling of Missing Data

The last observation before the day after final IMP administration will be carried forward if the measurement of the day after final IMP administration for the evaluation (efficacy and safety) at final administration time point is missing.

6 Primary and Secondary Endpoints:

6.1 Primary Endpoint

Tolvaptan exposure (C_{max} and AUC_{24h} on Day 1 of treatment period)

6.2 Secondary Endpoints

- Pharmacokinetics
Plasma concentrations and pharmacokinetic parameters of OPC-61815, tolvaptan, DM-4103, and DM-4107
- Pharmacodynamics
Serum concentrations of sodium and potassium, serum osmolality, biomarkers (plasma concentrations of arginine vasopressin [AVP] and brain natriuretic peptide [BNP], plasma renin activity, and serum concentrations of N-terminal pro-brain natriuretic peptide [NT-proBNP] and troponin), daily urine volume, daily fluid intake, daily fluid balance, daily urine sodium excretion, daily urine potassium excretion, and urine osmolality
- Efficacy
Body weight, congestive symptoms (lower limb edema, other edema, jugular venous distension, pulmonary congestion confirmed by chest X-ray, pulmonary rales, third

cardiac sound, and hepatomegaly), cardiothoracic ratio, and New York Heart Association (NYHA) classification

7 Disposition and Demographic Analysis

The following will be summarized by administration group (including the entire OPC-61815 group).

7.1 Subject Disposition

For subjects from whom informed consent was obtained (screened subjects), the number of subjects and the numbers and percentages of randomized subjects, subjects administered IMP, completed subjects after IMP administration, and discontinued subjects after IMP administration (the denominator indicates the number of randomized subjects) will be summarized. For discontinued subjects after IMP administration, the number and percentage of subjects by reason for discontinuation will be summarized.

For randomized subjects, the number and percentage of subjects included in each statistical analysis set will be summarized.

7.2 Demographic and Baseline Characteristics

For the pharmacokinetic analysis set, the subject population set of the pharmacokinetic analysis set for which at least one primary endpoint was obtained, and safety analysis set, descriptive statistics (number of subjects, mean, standard deviation, minimum, median, and maximum, the same applies hereinafter to Chapter 9) or distributions (number of subjects, %, the same applies hereinafter) will be calculated according to [Table 7.2-1](#).

Table 7.2-1 Demographic and Other Baseline Characteristics			
Variable	Time Point	Method	Level
Age	Informed consent acquisition	Descriptive statistics	-
		Distribution	20-29, 30-39, 40-49, 50-59, 60-69, 70-79, 80-85
			< 65, ≥ 65
Sex	-	Distribution	Female, Male, Undifferentiated
Height (cm)	Screening	Descriptive statistics	-
Body weight (kg)	Screening	Descriptive statistics	-

Table 7.2-1 Demographic and Other Baseline Characteristics			
Variable	Time Point	Method	Level
BMI (kg/m ²)	Screening	Descriptive statistics	-
Country	-	Distribution	JAPAN
Race	-	Distribution	Asian
Ethnicity	-	Distribution	Not Hispanic or Latino
Primary illness (multiple selection)	Screening	Distribution	Yes, No, Unspecified
• Ischemic heart disease			
• Non-ischemic cardiomyopathy			
• Valvular disease			
• Hypertensive heart disease			
• Arrhythmia			
Type of heart failure	Screening	Distribution	Right Heart Failure, Left Heart Failure, Bi-ventricular Failure, Unspecified
Presence of arrhythmia	Screening	Distribution	Yes, No
Use of Pacemaker	Screening	Distribution	Yes, No
Use of ICD	Screening	Distribution	Yes, No
Complication (multiple selection)	Screening	Distribution	Yes, No
• Hypertension			
• Angina pectoris			
• Diabetes mellitus			
• Renal impairment			
Presence of complication	Screening	Distribution	Yes, No
Presence of medical history	Screening	Distribution	Yes, No

